#### Secondary care

For reasons noted earlier, our analysis in secondary care will be a more limited feasibility study. We plan to work with Salford Royal NHS Foundation Trust, who have agreed in principle to take part in the study and to provide data from their Electronic Patient Record system. Salford is a Digital Exemplar, and one of the highest scoring NHS trusts on the NHS Improvement digital maturity index. We have an established working relationship from prior research(48, 49)and we know they have comprehensive EPR datasets which capture a wide range of clinical activity at the patient level. The EPR contains specific information relating to prescriptions (BNF code, dosage details and if the prescription was changed or omitted) which is in addition to more standard information about the hospital admission (patient age, gender, admission type, days since admission). Importantly the EPR also includes a medical staff identifier which our feasibility work indicates can be used to distinguish between locum and non-locum doctors, and to describe how much of a patient's care/treatment was provided by locums.

We will use pseudonymised data extracted from the electronic inpatient record system (EPR) and linked to electronic and manual records that identify locum and permanent doctors through their EPR identity code. We will use this data to determine the scale and scope (RQ1) of locum use including how it varies between specialties/departments, across the working week and out of hours. As with previously described WPs this aspect will focus on descriptive analysis and the identification of time trends.

To understand how clinical practice and performance (RQ3) may differ for locums is complex because patients receive care from both locum and permanent doctors during an inpatient stay. To appropriately attribute activity and outcomes to care provided by a locum we will take two approaches.

First, we will focus on prescribing activity which can be linked to a single locum. Specifically, by comparing prescribing practices using both established prescribing safety indicators developed for primary care but adapted for this setting(50) and EPR data on rates and outcomes of clinical pharmacist reviews/interventions (i.e. if the prescription is changed). Multivariate regression analysis will be used and safety indicators /pharmacist review outcomes will be the dependent variable. The independent variable will be binary, indicating whether the activity was performed by a locum. We will control for patient and ward characteristics which may be prescribing outcomes and treatment by locum (for example age, gender, speciality).

Our second approach will consider each entire patient admission and approximate the proportion of care delivered by locum doctors. For example if during their admission a patient has two interactions (such as tests or prescriptions) recorded by a locum doctor but six ordered by a permanent doctor, the proportion would be 0.25. This measure will be used as the independent variable when examining length of stay, rates of emergency readmission and mortality. With this analysis occurring in one trust only we will carefully consider if we have the power to detect meaningful associations. If under-powered, the processes developed could be applied to more trust EPR data in the future. Indeed, having undertaken this work successfully with Salford Royal NHS Foundation Trust, we will if time and resources allow seek to extend it to other hospitals in the Northern Care Alliance Group with similar EPR capabilities.

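### In the hospital feasibility study, the pharmacist-review outcome depends partly on pharmacist cover when the prescription was written, and the stated adjustment leaves out time of prescribing

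*Protocol*

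**What the plan says.** Protocol section 5, WP4, Secondary care, sets out two approaches to attributing hospital care to locums. The first concerns prescribing and uses two sources of outcome side by side. One is "established prescribing safety indicators developed for primary care but adapted for this setting". The other is "EPR data on rates and outcomes of clinical pharmacist reviews/interventions (i.e. if the prescription is changed".

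The regression is described briefly: "safety indicators /pharmacist review outcomes will be the dependent variable". On the exposure: "The independent variable will be binary, indicating whether the activity was performed by a locum". On adjustment: "We will control for patient and ward characteristics which may be prescribing outcomes and treatment by locum (for example age, gender, speciality".

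Earlier in the same section, the plan uses the same record system to describe the scale of locum use, including "how it varies between specialties/departments, across the working week and out of hours". The prescription fields it lists are "BNF code, dosage details and if the prescription was changed or omitted"; no field for review status is named there. The section states its own limits: "our analysis in secondary care will be a more limited feasibility study".

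The protocol does not say whether the pharmacist outcome is taken over all prescriptions or only over reviewed ones. It gives no review rate and no figure for when locums work.

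**The concern.** A pharmacist's change to a prescription is a detected event. It needs something to correct and a pharmacist who looks. The second condition depends on when and where the prescription was written and on whether it is still active when a pharmacist reaches it. None of these measures the prescriber's quality.

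The plan nevertheless uses both how often pharmacists review or intervene and what results as a comparison of prescribing. A review rate describes pharmacist activity at least as much as prescriber performance. A high rate could mean mostly weekday work, or closer scrutiny of locums' orders.

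The adjustment covers patients and wards. Time of prescribing is a property of neither, and specialty does not stand in for it, because one ward has both well-covered and thinly covered hours. The team treats timing as relevant when describing locum use but does not carry it into the comparison. At stake is the sign of the locum effect on this outcome, in an analysis that addresses RQ3 and may be extended to other hospitals.

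**Working it through.** The protocol states no figure for this analysis, so there is nothing to reproduce. The check asks how large a spurious difference could be when prescribing is identical in both groups.

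**Inputs, all assumed.**
- Share of prescriptions written in hours: s
- Probability of pharmacist review: r_in in hours, r_out out of hours
- Probability that a reviewed prescription is changed: c, equal for locum and permanent doctors

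**Formulas.**
- P(reviewed) = s × r_in + (1 − s) × r_out
- P(changed, over all prescriptions) = c × P(reviewed)
- P(changed, among reviewed) = c

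**Case 1.** r_in = 0.90, r_out = 0.40, c = 0.10; s = 0.80 for permanent doctors and 0.40 for locums.
- Reviewed, permanent: 0.80 × 0.90 + 0.20 × 0.40 = 0.80
- Reviewed, locum: 0.40 × 0.90 + 0.60 × 0.40 = 0.60
- Changed over all: 8.0% v 6.0%
- Odds ratio, locum v permanent: (0.060/0.940) / (0.080/0.920) = 0.73
- Shares swapped: the inverse, 1.36

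**Case 2, milder.** r_out = 0.70; s = 0.80 v 0.50.
- Reviewed: 0.80 × 0.90 + 0.20 × 0.70 = 0.86, against 0.50 × 0.90 + 0.50 × 0.70 = 0.80
- Changed over all: 8.6% v 8.0%
- Odds ratio: (0.080/0.920) / (0.086/0.914) = 0.92
- Shares swapped: 1.08

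**Wider range.** With r_in = 0.90, the table gives the ratio of proportions changed over all prescriptions, locum to permanent. Here c cancels. Example: out-of-hours shares of 60% v 30% with r_out = 0.50 give (0.4 × 0.9 + 0.6 × 0.5) / (0.7 × 0.9 + 0.3 × 0.5) = 0.66/0.78 = 0.85.

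| Out-of-hours share, locum v permanent | r_out 0.70 | r_out 0.50 | r_out 0.30 |
|---|---|---|---|
| 80% v 20% | 0.86 | 0.71 | 0.54 |
| 60% v 30% | 0.93 | 0.85 | 0.75 |
| 50% v 50% | 1.00 | 1.00 | 1.00 |
| 30% v 60% | 1.08 | 1.18 | 1.33 |

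If cover is the same at all hours (r_out = 0.90), every ratio is 1.00.

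**What removes the artefact.** In Case 1, stratifying by time gives 0.10 × 0.90 = 9.0% changed in hours and 0.10 × 0.40 = 4.0% out of hours in both groups, so the odds ratio is 1.00 in each stratum even over all prescriptions. Restricting to reviewed prescriptions gives c = 10% in both groups, again 1.00. The first result requires that, within a time stratum, review does not depend on locum status. The second requires that review is unrelated to the risk of error within each group.

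**The case against.** The strongest defence is that an outcome of a review presupposes a review. On that reading the denominator is already reviewed prescriptions, and the calculated bias disappears. The denominator is also a detail that an analysis plan could settle. This stands in part: a reader might infer that unreviewed prescriptions are counted as good, but the text does not say so. It is one reading, made plausible by the listing of change as a prescription field and by the interest in rates.

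A reader might also infer that a hospital prescription counts as a problem only when a pharmacist changes it. The documents do not support that, because the safety indicators are a parallel outcome. Nor do they support the inference that locums will look safer: no statement says that locums work more out of hours or that review is sparser then, and the direction reverses if the pattern does.

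Two further points for the defence have some weight. The covariates named are examples, so time could be added, and the sentence naming the dependent variable lists review outcomes but not rates. However, the stated class of adjustment is patient and ward characteristics, which time of prescribing falls outside. Review rates are still listed among the means of comparing prescribing. Comparing them would reveal differences in cover, but the plan presents them as prescribing practice, not as a check on detection.

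**Conclusion.** The concern holds for one of the two prescribing outcomes. Followed as written, the plan can give a spurious locum difference on the pharmacist-review outcome, in either direction, if locum use and pharmacist cover both vary over the week. The illustrative odds ratios of 0.73 and 0.92, with their inverses, rest wholly on assumed review rates and working patterns and on an all-prescriptions denominator. With equal patterns or equal cover there is no bias from this source. Reading review rates as prescriber performance is a problem whichever denominator is used.

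The consequence is limited, because this is a feasibility analysis and the main comparison of locum and permanent doctors is in primary care. It still merits correction before data extraction, since the method may be carried to other hospitals.

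**What to change.** In Protocol section 5, WP4, Secondary care (first approach):

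1. Add time of prescribing (in hours, evening or night, weekend) from the electronic record to the adjustment set, or stratify by it.
2. Where review status can be extracted, define the outcome as changed among prescriptions with a recorded pharmacist review, and keep all prescriptions as a sensitivity analysis.
3. Report the probability of review by group and time stratum as a description of ascertainment, not as prescriber performance.
4. Interpret the pharmacist outcome alongside the safety indicators.

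The cost is small if timestamps and review status are available: one more covariate and a stated denominator. The disadvantages are fewer prescriptions in the analysis and estimates that apply to reviewed prescriptions only. Bias remains if pharmacists target higher-risk prescriptions or look harder at locums' orders; neither the time stratum nor the restricted denominator removes that, and the report should say so.

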### WP4: Collection and analysis of existing/routine quantitative data sets to compare locum and permanent doctor practice/performance in primary and secondary care (RQ3)

Most routine/existing NHS datasets do not contain sufficient information to distinguish reliably between care provided by locum and non-locum doctors, and so our approach to quantitative analysis makes careful and informed use of selected datasets in which our pilot work has established this analysis is feasible, in order to address RQ3. Locum doctors can be identified either where the staff role is explicitly coded in the data set as a locum, or where records contain medical staff identifiers which can be linked to staffing/HR databases. However, especially in team settings where care may be provided by a number of medical staff including both locums and permanent doctors, it is difficult both to identify and to distinguish the distinctive contribution of locum doctors. For example, an activity (such as admission, discharge, test ordering, prescribing, operative procedure, etc) may be recorded by one member of a team (whether a locum or permanent doctor) but may have been initiated by another.

For this reason, out our quantitative analyses will focus primarily on primary care, where the quality of data is high, locum information is known to be reliably collected and available in CPRD, and the attribution of activities to individual doctors (whether permanent or locum) is less problematic. However, we also set out plans for a more limited feasibility study in

secondary care, using Electronic Patient Record (EPR) data from one NHS trust with the capacity to extend the analysis to others.

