Data will be complete (e.g. a patient either is coded as having diabetes or not) and of high quality since tied to financial incentives (e.g. QOF) or almost impossible not to record (e.g. consultation, or prescribing). Therefore, we will not need to use a multiple imputation framework or anything similar. Confounding is a concern, with urgent requests perhaps being more likely handled by locums – e.g. a patient cannot afford to wait for 2 weeks before his/her regular GP is back from holiday. We will partly attempt to control for that through the available patient characteristics, but we will also interpret our results with caution and use the recently suggested E-Value to assess the potential effect of unmeasured confounding.(47) The age of GPs is not available in the database, and another concern is that locums may be much less experienced that permanent GPs, hence any potential differences could be attributed to that rather than the locum status. Although we need to be careful not to "overcontrol" the analyses for the characteristics of locum GPs, since numerous GPs close to or in retirement choose to locum, we will conduct a sensitivity analysis where we will exclude more experienced permanent GPs (thus focusing on GP registrars, salaried GPs and GP retainers vs locums, repeating all analyses previously described).

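### The hospital prescribing model adjusts for patient and ward but for nothing about the prescriber, so a seniority difference may be reported as a locum effect or may hide one

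*Protocol*

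**What the plan says.** The first approach in Protocol Section 5, WP4, Secondary care, takes prescribing as the activity that can be tied to one doctor. On the outcome it says "safety indicators /pharmacist review outcomes will be the dependent variable". On the exposure it says "The independent variable will be binary, indicating whether the activity was performed by a locum". On confounding it says "We will control for patient and ward characteristics", with age, gender and speciality as examples.

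The only prescriber information the section plans to obtain is locum status. EPR data are to be "linked to electronic and manual records that identify locum and permanent doctors through their EPR identity code". The WP4 introduction describes this route in general terms, as one used "where records contain medical staff identifiers which can be linked to staffing/HR databases".

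The primary care part of WP4 treats the same contrast differently. It lists practitioner characteristics as a class of covariate beside patient and practice, and notes that GP age and sex are not available. It then warns that "another concern is that locums may be much less experienced that permanent GPs", so that a difference might be due to experience and not to locum status. It responds in two ways: "we will conduct a sensitivity analysis where we will exclude more experienced permanent GPs", and an E-value is to be used for unmeasured confounding generally. Both are written for primary care only.

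**The concern.** The exposure is a property of the prescriber, but no other property of the prescriber enters the hospital model. Seniority is an obvious candidate confounder. It could plausibly affect what is prescribed and how often a pharmacist changes it, and it may be distributed differently among locums and other doctors. Specialty and ward do not stand in for it, because one ward can have prescribers of several grades.

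This is the one hospital analysis that the protocol regards as attributable to an individual doctor, and it is offered as evidence on RQ3 (how locum and permanent doctors compare). If it were confounded by seniority, an apparent locum effect could be spurious and an apparent absence of one could be false reassurance. The method is also meant to be reusable at other trusts, so the omission could be carried forward.

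**Working it through.** **1. Does the wording leave room for grade?** The adjustment sentence reads "We will control for patient and ward characteristics which may be prescribing outcomes and treatment by locum (for example age, gender, speciality", and the bracket then closes. The list of examples is open, but only within patient and ward characteristics. A prescriber's grade is neither. Nothing else in the hospital section names grade or experience as a covariate, a stratifier or a sensitivity analysis. An analysis plan that followed this sentence faithfully would leave it out.

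**2. The two settings side by side**

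| | Primary care | Hospital prescribing |
|---|---|---|
| Classes of covariate | patient, practitioner, practice | patient, ward |
| Experience named as a rival explanation | yes | no |
| Analysis addressing experience | sensitivity analysis by GP type | none stated |
| E-value | yes | none stated |

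**3. How large could the effect be?** The protocol gives no event rate, grade mix, sample size or power for this analysis, so there is no figure to reproduce. Everything below is an assumption, chosen only to show the mechanism.

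Let p_J and p_S be the rates of flagged or changed prescriptions for junior and senior prescribers, the same for locums and others within grade (true odds ratio 1). Let f be the share of a group's orders written by juniors. Then

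- group rate: r = f × p_J + (1 − f) × p_S
- crude odds ratio: OR = [r_L / (1 − r_L)] / [r_P / (1 − r_P)], with L for locum and P for permanent.

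Take p_J = 12%, p_S = 6%, and f = 0.8 for permanent doctors:

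- Permanent: 0.8 × 12 + 0.2 × 6 = 10.8%.
- Locums with f = 0.4: 0.4 × 12 + 0.6 × 6 = 8.4%. OR = (0.084/0.916) / (0.108/0.892) = 0.76.
- Locums with f = 1: 12.0%. OR = (0.120/0.880) / (0.108/0.892) = 1.13.

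Other assumed inputs:

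| Junior share, locum v permanent | OR at 10% / 5% | OR at 9% / 6% |
|---|---|---|
| 50% v 50% | 1.00 | 1.00 |
| 60% v 50% | 1.07 | 1.04 |
| 70% v 50% | 1.15 | 1.09 |
| 80% v 50% | 1.22 | 1.13 |
| 70% v 30% | 1.34 | 1.19 |
| 30% v 50% | 0.86 | 0.91 |
| 30% v 70% | 0.75 | 0.84 |

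**4. Masking.** Return to the 12% / 6% rates with f = 0.4 for locums and 0.8 for permanent doctors, and suppose a true within-grade OR of 1.32.

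- Junior locum odds: 0.12/0.88 × 1.32 = 0.180, a rate of 15.3%.
- Senior locum odds: 0.06/0.94 × 1.32 = 0.0843, a rate of 7.8%.
- Locum rate: 0.4 × 15.3 + 0.6 × 7.8 = 10.8%, the same as for permanent doctors.

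The crude OR is then about 1.00, although a locum effect is present.

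**5. What the planned adjustment already removes.** These are crude odds ratios. If f is equal for locum and permanent orders within every specialty and ward, then r_L = r_P within each of them and the adjusted OR is 1.00. Only an imbalance that remains within specialty and ward can bias the planned estimate. The protocol gives no information on that remainder.

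**The case against.** The strongest case on the other side has five parts.

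*The harm is not shown.* A reader might infer that a seniority difference will be reported as a locum effect. The protocol does not support that. It gives no grade mix for hospital locums or their comparators, and nothing linking grade to the outcomes. Its background says that locums cover rota gaps and shortage specialties, which does not imply a different grade mix within a specialty. A reader might also take the comparator to be every doctor from trainee to consultant. The hospital section refers only to permanent and non-locum doctors and does not say which grades that includes. Both objections stand, so the point is put as a possibility.

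*It is a feasibility study.* WP4 puts its quantitative weight on primary care. This lowers the importance of the result but does not remove the confounding. A feasibility stage is also a good time to learn whether grade can be obtained.

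*The exact covariate set belongs in an analysis plan.* That would be a fair answer if the list were simply open. The protocol has fixed the class of covariate, and the class excludes the prescriber.

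*Overcontrol and estimand.* The primary care section warns against adjusting away characteristics of locums, and RQ3 can be read as asking for the overall contrast. This is a sound reason not to replace the planned model. It is no reason against showing a grade-conditional result beside it, much as the sponsor does for GPs.

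*Grade may be unobtainable or misattributed.* Nothing shows that the linked records hold grade. The WP4 introduction also warns that the doctor who records an activity, prescribing included, may not be the one who initiated it. Both limits stand and bear on the remedy.

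**Conclusion.** The point holds in a conditional form. As written, the hospital prescribing model cannot separate locum status from seniority, and the protocol does not apply there the safeguards it provides against the same threat in primary care. Whether this produces bias rests on two conditions that the protocol neither states nor excludes: that grade mix differs between locum and non-locum prescribers within specialty and ward, and that grade affects the safety indicators or pharmacist changes. If either fails, there is no bias from this source.

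Direction and size are unknown. The illustrations run from about 0.75 to 1.34 with no true effect, and mild imbalances (60% v 50%) give only 1.04 to 1.07. All rest on assumed rates and mixes before specialty or ward adjustment, and none is an estimate for this trust. The point merits a change to the plan, in proportion to an analysis of feasibility status.

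**What to change.** In WP4, Secondary care, first approach:

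1. Request prescriber grade through the linkage of EPR identity codes to staff records that is already planned.
2. Report a grade-adjusted or within-grade comparison of locum and non-locum prescribers beside the patient- and ward-adjusted model. Showing both lets the reader see the overall and the grade-conditional contrast, which meets the overcontrol concern.
3. If grade is unavailable, or largely missing for locums, do not rely on an unknown-grade category. If missing grade is concentrated among locums, that category would nearly duplicate the exposure. Instead apply the E-value from the primary care section to this analysis, and limit the conclusion to a difference that cannot be separated from seniority.

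The cost is one extra field in the linkage request and one further model per outcome. That the records contain grade is an assumption, and it may be missing more often for locums. Because the recording doctor may not have initiated the prescription, even a complete grade field would remove confounding by seniority only in part; the report should say so.

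### WP4 secondary care: the whole-admission locum share stops accruing at discharge or death, so the length-of-stay and in-hospital mortality regressions can show a locum effect where none exists if locum use varies by phase of stay.

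*Protocol*

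**What the plan says.** The point concerns the second of two approaches in the Protocol, section 5, WP4, Secondary care. The exposure window is the full stay: "Our second approach will consider each entire patient admission and approximate the proportion of care delivered by locum doctors". The worked example fixes the ratio: with "two interactions (such as tests or prescriptions) recorded by a locum doctor but six ordered by a permanent doctor, the proportion would be 0.25". Its use is also fixed: "This measure will be used as the independent variable when examining length of stay, rates of emergency readmission and mortality".

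The same section explains that attribution is difficult because "patients receive care from both locum and permanent doctors during an inpatient stay". It plans to describe locum use, including "how it varies between specialties/departments, across the working week and out of hours". The fields listed for the electronic record include "patient age, gender, admission type, days since admission". It also sets the status of the work: "our analysis in secondary care will be a more limited feasibility study".

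For this approach the section states no early exposure window, no landmark and no time-updated exposure, and it does not say how death as the end of a stay is handled. Its only caution here is about power. The period over which mortality is counted is not given.

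**The concern.** Both parts of the ratio build up until the patient leaves or dies. For length of stay, the outcome itself sets how many later interactions enter the denominator, and what mix of early and late care the share averages over. For in-hospital death, interactions prompted by the final deterioration are counted as exposure, although they are part of the process that ends in death.

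Suppose locums carry more of the work at intake. Short stays then have a high share simply because they consist mostly of intake, and locum care appears to shorten stays. If locums carry more of the later work, the sign reverses. Adjusting for age, gender, specialty or ward does not help, because the distortion comes from when the exposure stops accruing and not from differences between patients. More data would make the wrong estimate more precise. At stake is whether this analysis can attribute length of stay and in-hospital death to locum care at all.

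**Working it through.** **The plan's own figure.** 2 / (2 + 6) = 0.25. This reproduces.

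**Why the share moves with length of stay.** The documents give no locum shares, interaction rates or stay lengths, so all inputs here are assumptions. Take 5 interactions on day 1 and 2 on each later day, with locum share p1 on day 1 and p2 afterwards. For a stay of L days,

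expected share = [5·p1 + 2(L − 1)·p2] / [5 + 2(L − 1)].

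| p1, then p2 | L = 1 | L = 6 | L = 11 |
|---|---|---|---|
| 20%, 10% | 1/5 = 20.0% | 2/15 = 13.3% | 3/25 = 12.0% |
| 10%, 20% | 0.5/5 = 10.0% | 2.5/15 = 16.7% | 4.5/25 = 18.0% |
| 15%, 15% | 15.0% | 15.0% | 15.0% |

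Locums affect nothing in this set-up, yet share and stay are related in the first two rows.

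**Size of the false slope.** Simulated admissions with no locum effect, gamma-distributed stay with mean 5.9 days and shape 1 to 3, and the interaction rates above. Linear slope of days on share:

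| Locum share, day 1 then later | False slope, days per 10 points |
|---|---|
| 20% then 10% | about -0.45 to -0.76 |
| 12% then 10% | about -0.13 to -0.24 |
| 10% then 20% | about +0.45 to +0.99 |
| Constant 15% | about 0 |
| Day-1 share as exposure | about 0 |

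**A second set-up.** Geometric stay with mean 5 days, 3,000 admissions, 300 runs, no locum effect, log length of stay regressed on the whole-stay share:

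| Locum share | Length-of-stay ratio per 0.25 share | Runs significant at 5% |
|---|---|---|
| Constant 15% | 1.00 | 3% |
| First day 20%, later 15% | 0.86 | 100% |
| First day 25%, later 10% | 0.67 | 100% |
| First day 10%, later 20% | 1.48 | 100% |
| Weekend 30%, weekday 10%, admissions even over the week | 1.00 | 3% |

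With the first-day share as exposure in the same data, the mean slope was about 0 and 2% to 6% of runs were significant.

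**In-hospital death.** There are two routes.

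- Deterioration: assume a 10% locum share in hours, 30% out of hours, and 1 to 4 extra out-of-hours interactions before death. The false odds ratio is about 1.06 to 1.21 per 10 points of share.
- Timing alone: 5,000 admissions, 200 runs, daily competing hazards of death and discharge, locum share 25% on the first day and 10% later. Deaths concentrated early give an odds ratio of 1.45 per 0.25 share; deaths concentrated late give 0.75. With a constant 15% share it is 0.99. With first-day exposure it is 0.99 to 1.00.

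These runs test the exposure window. They do not test the full landmark or competing-events models proposed below.

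**The case against.** The strongest reply is that the bias is conditional and the protocol does not establish the condition. The planned description of locum use across the week and out of hours is an aim, not a finding, and it says nothing about day of stay. This stands. A constant share gives no bias in the slope, nor does pure weekend variation with admissions spread evenly. A reader might infer that the coefficients can never be read as a locum effect; the documents do not support that. The protocol does, however, treat the pattern of locum use as unknown, so it cannot rely on the benign case.

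Second, the work is labelled a feasibility study, the measure is called approximate, and primary care carries the main comparison. That lowers the stakes but does not alter how the exposure accrues. Extension to other hospitals is conditional on time and resources, so it should not be presented as certain.

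Third, the model may be specified in an analysis plan not seen here. Model form and covariates may well be. The exposure window and its use against these outcomes are already set in the protocol.

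Fourth, the outcomes differ. The quoted sentence lists readmission with the others, and a reader might infer that all three are equally affected. Readmission and death after discharge come after the exposure is complete and are touched at most indirectly, through length of stay.

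Finally, it is tempting to show the problem by comparing stays above and below a 25% share. That should not be done. At a constant 15% share the two groups already differ, about 3.7 to 4.9 against 6.1 to 6.4 days, largely because short stays have small denominators and noisy shares. The plan uses the proportion itself and has no such cut.

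**Conclusion.** The point holds in conditional form, for length of stay and in-hospital death. The protocol's exposure rule lets the outcome help determine the exposure. A false locum effect of either sign follows if locum share differs between early and later care, or if deterioration before death brings in locums. If locum share is unrelated to phase of stay, the linear slope is about unbiased.

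The size in the trust's data cannot be derived from the documents. The sign depends on how locums are rostered. Under the assumed inputs even a small gradient, 12% then 10%, gives roughly -0.13 to -0.24 days per 10 points. The mortality range depends further on the baseline out-of-hours fraction and the number of extra calls, and other inputs could move it outside 1.06 to 1.21. The change should be made, but this is a secondary, feasibility-stage analysis and the main primary care comparison is unaffected.

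**What to change.** For length of stay and in-hospital death, replace the whole-admission share in one of two ways.

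1. Use the cumulative locum share up to the previous day as a time-varying exposure, with days since admission as the time scale and discharge and death as competing events.
2. Use the share in a fixed early window, restrict the analysis to patients still in hospital at the landmark, and count outcomes from then.

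State the mortality window, and separate in-hospital from post-discharge death. Keep the whole-stay share as a descriptive measure of how much care locums give. It may also serve for readmission, with its indirect dependence on length of stay acknowledged.

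The cost is mainly re-coding: days since admission is already among the listed fields, and interactions would need to be dated within the stay. The landmark version loses stays that end before the landmark and answers a narrower question, about early locum care only. The time-varying version keeps more of the original question but needs more modelling. Neither removes confounding by severity; if patients deteriorate over several days and locums are called, a one-day lag only reduces the problem, and the report should say so.
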